4.2 SCIENTIFIC RATIONALE FOR STUDY DESIGN

The experimental treatment arm (Group A2) will receive an add-on therapy given on top of existing SOC induction therapy and the control groups will receive SOC induction therapy alone. This will be a superiority study to demonstrate that add-on antibiotic therapy is superior to existing standard of care.

The control arms (Group A1 and B) are stratified based on microbiome profile. This will allow us to confirm our previous observations that subjects with a relapse-associated microbiome profile are at an increased risk of relapse after completing induction therapy. The primary objective will be to compare the rates of sustained remission between Groups A1 and A2 to determine whether add-on antibiotic therapy improves outcomes for patients with a relapse-associated microbiome profile. Group C will allow patients to receive additional antibiotic for a separate indication of induction of remission, as this group has not received clinical remission on nutritional therapy alone by week 4.

4.3 JUSTIFICATION FOR DOSE

Azithromycin and metronidazole will be administered orally as a tablet as according to their FDA-approved labels, or as a suspension if required (see Attachments). Both azithromycin and metronidazole are available in 250mg tablets, doses will be given in multiple of 125mg (1/2 tablets).

Azithromycin will be administered at a dose of 7.5mg/kg to a maximum of 500mg/day for 5 consecutive days per week for the first 4 weeks and then 3 consecutive days/week for 4 weeks. Metronidazole will be administered 10mg/kg twice daily to a maximum of 1000mg/day for 8 weeks. There will be no placebos administered in this study. These dosages are based on the recent RCT of azithromycin + metronidazole.²¹

4.4 END OF STUDY DEFINITION

A participant is considered to have completed the study if he or she has completed all phases of the study including the last visit or the last scheduled procedure shown in the Schedule of Activities (SoA), Section 1.3.

The end of the study is defined as completion of the last visit or procedure shown in the SoA in the trial globally.

5 STUDY POPULATION

5.1 INCLUSION CRITERIA

In order to be eligible to participate in this study, an individual must meet all of the following criteria:

1. Provision of signed and dated informed consent form (and assent form, as applicable)
2. Stated willingness to comply with all study procedures and availability for the duration of the study
3. Male or female, aged 3 to 17 years
4. Diagnosed with CD according to standard clinical and histological criteria, within 36 months of week 0

5. Exhibiting mild to moderate symptoms of active disease, as determined by a PCDAI score >10 (or >7.5 excluding the height item) and ≤37.5
6. Evidence of active inflammation based on either: fecal calprotectin level >=250 microgram/g (local laboratory or pre-arranged sponsor testing) within 30 days prior to week 0 visit; or according to accepted endoscopic and histologic evidence obtained during an endoscopy procedure completed within 30 days prior to Week 0 Visit.

5.2 EXCLUSION CRITERIA

An individual who meets any of the following criteria will be excluded from participation in this study:

1. Current or previous use of anti-TNF or other biologic therapy
2. Presence of stricturing, penetrating (intestinal or perianal) and/or fistulizing CD.
3. Pregnancy or lactation
4. Have undergone intestinal resection
5. Laboratory diagnosis of Clostridium Difficile Infection (CDI), if performed for clinical indication
6. Treatment with another investigational drug or other intervention within 30 days before week 0
7. Risk factors for arrhythmia including history of prolonged QTc, hypokalemia or hypomagnesemia, resting bradycardia, or concurrent treatment with other drugs with potential for QT prolongation.
8. History of Cockayne syndrome
9. Prior diagnosis of any hematologic condition/blood dyscrasia which may result in leukopenia (even if leukocyte count is normal at screening)
10. Known allergy or intolerance to azithromycin or metronidazole
11. Subjects who received IV anti-infective within 35 days prior to week 0 visit or oral anti-infectives within 14 days prior to the week 0 visit.
12. Subject on oral aminosalicylates who has not been on stable doses for greater than, or discontinued within, at least 14 days prior to week 0.
13. Subject on cyclosporine, tacrolimus or mycophenolate mofetil. Stable doses (no change within 14 days prior to week 0) of Azathioprine, 6-mercaptopurine or MTX are not a reason for exclusion.
14. Subject who received fecal microbial transplantation within 35 days prior to week 0 visit.
15. Screening laboratory and other analyses show any of the following abnormal results:
 - AST, ALT > 2 X upper limit of the reference range (as determined locally at each site)
 - Urea, Creatinine > 1.5X upper limit of the reference range (as determined locally at each site)
 - White blood cell (WBC) count < 3.0 X 10⁹/L
 - Total bilirubin >= 20 micromol/liter (1.17mg/dl); except for subjects with isolated elevation of indirect bilirubin relating to Gilbert syndrome
 - Hemoglobin < 80 gram/liter
 - Platelets < 100,000/ μ L

Note: The laboratory markers of e.g. AST and ALT are deliberately specified relative to upper limit of normal as these values (and units used) differ between the different labs within the USA and across the study sites in the USA, Canada and Europe.

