1.3 SCHEDULE OF ACTIVITIES (SOA)

Procedures	Visit 1 Screening ≤30 days prior to week 0	Visit 2 Week 0	Study Visit 3 Week 4	Study Visit 4 Week 12	Study Visit 5 Week 24	Study Visit 6 Week 36	Final Study Visit 7 Week 52
Informed consent	X						
Demographic data	X						
Medical history	X	X	X	X	X	X	X
Review inclusion/exclusion criteria	X	X					
Concomitant medication review	X	X	X	X	X	X	X
Physical exam (including height and weight)	X	X	X	X	X	X	X
Medication calendar distribution and teaching		X					
Blood sample ^a	X	X ^b	X	X	X	X	X
Calculate PCDAI score (0-100)	X	X ^b	X	X	X	X	X
Stool sample (16S rRNA)	X	X ^b	X	X	X	X	X
Stool sample (FCP)	X	X ^b	X	X	X	X	X
Stool sample (C. difficile infection testing) ^c	X						
Urine pregnancy test ^d	X		X				
Adverse event review and evaluation			X	X	X	X	X
Randomization			X				
ECG, if applicable ^e			X				
Administer antibiotic, if applicable			X				
Teaching for antibiotic medication calendar, if applicable			X				
Complete Case Report Forms (CRFs)	X	X	X	X	X	X	X
IMPACT (ages 9 and older)		X		X	X		X

A window of study timepoint +/- 5 days is allowed for all visits/questionnaires/sampling.

a: Includes hematology and clinical chemistry Albumin, C reactive protein (CRP), hematocrit (HCT), erythrocyte sedimentation rate (ESR), alanine transaminase (ALT), aspartate transaminase (AST), creatinine, and bilirubin. Total blood volume collected at each visit will be 5ml.

b: The timing of the Screening and Week 0 visits will depend on the start of therapy. Week 0 blood and stool samples will not be repeated if provided during the screening visit, provided that the stool samples were collected prior to bowel prep.

c: If performed for clinical indication, as per standard of care

d: Only applicable for post-menarchal female participants initiating methotrexate

Procedures	Visit 1 Screening ≤30 days prior to week 0	Visit 2 Week 0	Study Visit 3 Week 4	Study Visit 4 Week 12	Study Visit 5 Week 24	Study Visit 6 Week 36	Final Study Visit 7 Week 52
e: All patients randomized to group A2 and C will receive an ECG exam both prior to and at 2-4 weeks after the initiation of the study drug							

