8 STUDY ASSESSMENTS AND PROCEDURES

8.1 EFFICACY ASSESSMENTS

History and Physical exam – These will be performed as per the standard of clinical care including height (height velocity), weight and perianal inspection. The primary outcome variable will be whether sustained remission at 52 weeks after starting standard of care induction therapy is achieved. Sustained remission is not defined by PCDAI alone; but rather by PCDAI ≤ 10 at week 52 AND not having need of re-induction for clinical flare (new course of EEN, need to start steroids), no steroid dependence, no biologic (anti-TNF) use, and no intestinal surgery by 12 months. As secondary outcome variables of efficacy, longitudinal (clustered and with respect to baseline) changes in disease activity indices components, and inflammatory markers in blood and stool, will be collected including the PCDAI score (0-100), normalization of CRP (<0.5 mg/dL or the local reference range as applicable), fecal calprotectin (microgram/g) and Delta-fecal calprotectin before and after the study intervention. In addition, longitudinal (clustered and with respect to baseline) changes of Patient-reported outcome will be collected (IMPACT (self-report, ages 9-17 years).

Blood samples – Blood samples will be drawn as per the standard of clinical care including erythrocyte sedimentation rate (ESR), C-reactive protein, albumin, alanine transaminase (ALT), aspartate transaminase (AST), bilirubin, Urea (Blood Urea Nitrogen (BUN) and Creatinine,)and complete blood count (including hematocrit). These blood results, provided by the local clinical labs, will be required to calculate the disease activity index and monitor for toxicity due to methotrexate.

Stool samples – For assessment of inclusion criteria for Screening, stool samples will be obtained for local testing for the presence of toxicogenic *C. difficile*. This sample may be a pre-consent sample collected as standard of care. Study stool samples will be collected at each study visit and split into two aliquots; one for Fecal calprotectin testing and one for microbiome analysis at the central laboratory Dalhousie University (Integrated Microbiome Resource) as coordinated from Amsterdam UMC.

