8.2 SAFETY AND OTHER ASSESSMENTS

Electrocardiograms (ECGs): ECG is for screening purposes only to identify prolongation of QT (QTc) corrected for age appropriate norms. If there is prolongation, as identified by each responsible physician, then the responsible physician is responsible for communicating this finding with the patient and family and arranging appropriate follow-up with cardiology. Patients found to have QT prolongation will not be treated with investigational therapy and appropriate guidance will be given regarding avoiding other medication with the potential of QTc prolongation (e.g. avoiding ondansetron). Further, all patients randomized to group A2 will receive a follow-up ECG 2-4 weeks after the initiation of the study drug to ensure that new-onset QT prolongation is not occurring as a result of azithromycin treatment. If clinically significant QT prolongation is detected at follow-up ECG, patients should discontinue investigational therapy. If the subject is not in clinical remission at week 4, then the responsible physician will decide whether azithromycin/metronidazole can be started as additional induction therapy.

Blood samples: Blood drawn as per the standard of clinical care will be tested for alanine transaminase (ALT), aspartate transaminase (AST), bilirubin, BUN and Creatinine by the local clinical labs to monitor for toxicity due to methotrexate.

Urine pregnancy tests: A urine pregnancy test will be administered at screening and repeated at week 4 prior to the initiation of methotrexate in post-menarcheal female patients. These tests will be used to prevent exposure of participants to potential embryotoxic/teratogenic effects of methotrexate. Counselling and reinforcement of these potential risks and the importance of pregnancy prevention will be included at every study visit. Post-menarcheal patients will be counselled about the use of birth control to prevent unplanned pregnancy while taking methotrexate during this study period.

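### Exclusion 7 names low potassium and low magnesium as arrhythmia risk factors, but no supplied text requires either to be measured before azithromycin starts at week 4

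*Combined protocol and SAP*

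**What the plan says.** Section 5.2, item 7 excludes children with "Risk factors for arrhythmia including history of prolonged QTc, hypokalemia or hypomagnesemia, resting bradycardia" or with concurrent QT-prolonging drugs. It gives no threshold and no test for either electrolyte. Item 15 of the same section applies where "Screening laboratory and other analyses show any of the following abnormal results" and then sets its numerical limits.

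Blood work is described in three other places:

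- Section 1.3, footnote a, opens "a: Includes hematology and clinical chemistry Albumin, C reactive protein (CRP), hematocrit (HCT" and continues with a short list. It adds: "Total blood volume collected at each visit will be 5ml".
- Section 8.1: "Blood samples will be drawn as per the standard of clinical care including erythrocyte sedimentation rate (ESR), C-reactive protein, albumin", and further items. The stated purposes are the disease activity index and methotrexate toxicity.
- Section 8.2: ALT, AST, "bilirubin, BUN and Creatinine by the local clinical labs to monitor for toxicity due to methotrexate".

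On the cardiac side, footnote e of Section 1.3 says "All patients randomized to group A2 and C will receive an ECG exam both prior to and at 2-4 weeks" after the study drug is started. Section 8.2 says "ECG is for screening purposes only to identify prolongation of QT (QTc) corrected for age appropriate norms" and bars study treatment if the QT is prolonged. Section 2.3.3 rests the cardiac safeguard on rhythm screening before antibiotics.

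The Schedule of Activities marks eligibility review at screening and week 0. Randomization, ECG and the start of antibiotics fall at week 4. Medical history, medication review and a blood sample are also scheduled at week 4.

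**The concern.** The plan treats a low potassium or magnesium as reason enough to keep a child out, yet its named tests would not show one. A site that runs only the tests the text names could start azithromycin in a child with a deficit that nobody has looked for. The planned course is not brief: 5 days a week for 4 weeks, then 3 days a week for 4 weeks, which is 5 × 4 + 3 × 4 = 32 dosing days.

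What is at stake is the safety of individual children, not the validity of the comparison between A1 and A2. There is also a longer reach. The Netherlands addendum (Section 12) foresees no substantial change to the protocol before a full-scale trial if the pilot proves feasible, so the gap could carry forward.

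**Working it through.** The plan states no figure on this point, so the check sets the texts side by side and counts.

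**1. What each list names.**

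| Place | Items named | Count | Potassium or magnesium |
|---|---|---|---|
| Section 1.3, footnote a | albumin, CRP, HCT, ESR, ALT, AST, creatinine, bilirubin | 8 | none |
| Section 5.2, item 15 | AST, ALT, urea, creatinine, WBC, bilirubin, hemoglobin, platelets | 8 | none |
| Section 8.1 | ESR, CRP, albumin, ALT, AST, bilirubin, urea, creatinine, complete blood count | 9 | none |
| Section 8.2 | ALT, AST, bilirubin, BUN, creatinine | 5 | none |

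Result: 0 of 4 lists name either ion.

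**2. What exclusion 7 asks for.** The words 'history of' may govern only the QTc item or the electrolytes as well. If they govern both, taking a history satisfies the criterion, and a current unrecognised deficit is not sought. If they govern only QTc, a current deficit excludes, but no named test reveals it. The gap is the same on either reading.

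**3. Timing.** The last formal eligibility review is at week 0 and the first antibiotic dose is at week 4. Section 7.2 lets an investigator withdraw a child who newly meets an exclusion criterion, or whose meeting it was not recognised before. That acts only on a deficit that has been found.

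**4. What the ECG covers.** The pre-dose ECG detects QT prolongation already present. It does not measure either ion, and exclusion 7 lists the electrolyte deficits separately from prolonged QTc.

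**5. How many children a week 4 check would cover.** Antibiotic recipients R = A2 + C, with 20 enrolled (Section 4.1) and 1:1 allocation in blocks of 2 within group A (Section 6.3):

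- all 20 in B: R = 0
- all 20 in A: R = 20 / 2 = 10
- all 20 in C and all treated: R = 20

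**6. First results needed.** Two assays each, so 2 × R = 0, 20 or 40. If all 20 are in A and are tested before allocation is known, the count is 2 × 20 = 40. Repeats after correction and replacement children (Section 7.2) come on top, so 40 is not a ceiling.

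These counts bound the number of children to be checked. They say nothing about how many have a deficit.

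**The case against.** The strongest reply is that exclusion 7 can be applied as written. Its neighbours, items 8 to 10, rest on history, prior diagnosis or known intolerance. Laboratory limits are gathered in item 15. History and medications are reviewed at screening, week 0 and week 4. On this view the criterion concerns recognised conditions and the plan contradicts nothing.

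Silence is also weak evidence here. Footnote a and Section 8.1 are open-ended. Footnote a is plainly not exhaustive, since it does not name the WBC, hemoglobin, platelets or urea that item 15 needs. Bloods follow local standard care. The manual of procedures (mentioned in Section 10.1.10) and the attached azithromycin insert (Section 2.3.1) were not available for this review.

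There are further layers of protection: ECGs before and after starting, no treatment if the QT is prolonged, withdrawal for a laboratory abnormality (Section 7.2), physician discretion in group C, and safety board review at least semiannually. Children randomized to A2 are in clinical remission at week 4.

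Most of this stands, and it limits the severity. It rules out two stronger inferences a reader might draw. One is that potassium and magnesium will not be measured; the open-ended lists and the unsupplied manual prevent that conclusion. The other is that children will be dosed with a deficit; no frequency is given and the ECG may catch some of the risk. What does not stand is that the safeguards close the gap. Each acts on a prolonged QT or on a value someone already has, and none requires the measurement.

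**Conclusion.** The point holds as a modest safety gap: 0 of 4 lists name potassium or magnesium, and no formal eligibility review falls between week 0 and the first dose at week 4. A current unrecognised deficit need not be found before azithromycin starts.

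The population concerned is 0 to 20 of 20 children, depending on how they fall into groups A, B and C. The number actually affected is unknown and may be zero. The conclusion rests on the supplied text alone. If the manual already requires both tests before azithromycin, a cross-reference answers the testing part of the point.

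It would overstate the matter to call exclusion 7 unworkable or the cardiac plan unsafe. The criterion can be applied from history, and the ECG rules give real protection. The sample size, the Fisher's exact comparison of A1 with A2 and the ITT definition are untouched. This is an improvement the sponsor could make, not a condition for the trial to proceed.

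**What to change.** 1. Add serum potassium and magnesium to footnote a of Section 1.3 and to Section 8.2, at the existing week 4 draw, for children due to start azithromycin (A2 and C), with results seen before the first dose.
2. If either value is below the local lower limit, delay the antibiotic start until it is corrected, and count the 8-week course from the first dose rather than from week 4.
3. Reword the electrolyte part of exclusion 7 to *current uncorrected hypokalemia or hypomagnesemia*. Wording such as *known or history of* would bar a child whose past deficit has long been corrected, a needless loss in a 20-child pilot.
4. State in Section 7.2 that a week 4 deficit that is corrected is not a ground for withdrawal. Otherwise the new test would create a newly met exclusion criterion, which 7.2 now accepts as a reason to withdraw. The child stays in the assigned group and in the ITT analysis.

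The cost is two routine assays per antibiotic recipient (0 to 40 first results, plus repeats and replacements), an occasional short delay in starting antibiotics, and confirmation from each local laboratory that the 5 ml draw suffices. A child who starts late will still be on treatment at the week 12 tablet count, so adherence should be judged against the doses due by then.

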5.3 LIFESTYLE CONSIDERATIONS

Not applicable.

5.4 SCREEN FAILURES

Screen failures are defined as participants who consent to participate in the clinical trial but are not subsequently randomly assigned to the study intervention or entered in the study. A minimal set of screen failure information is required to ensure transparent reporting of screen failure participants, to meet the Consolidated Standards of Reporting Trials (CONSORT) publishing requirements and to respond to queries from regulatory authorities. Minimal information includes demography, screen failure details, eligibility criteria, and any serious adverse event (SAE).

Individuals who do not meet the criteria for participation in this trial (screen failure) because of incomplete clinical data or recent *Clostridium difficile* infection positivity may be rescreened. Rescreened participants should be assigned the same participant number as for the initial screening.

5.5 STRATEGIES FOR RECRUITMENT AND RETENTION

Potential participants will be identified by their treating gastroenterologist within 1 of 8 participating centres across the U.S.A., Canada, the Netherlands, and Israel. The study sites are pediatric gastroenterology clinics and participants will be recruited from patients who are undergoing diagnostic procedures and receiving medical treatment for Crohn's disease, as per standard of care.

For this pilot study, up to 5 participants from each site will be recruited until a total of 20 subjects. The treating gastroenterologist will ask the patient and their parent/guardian if they are interested in hearing more about the study and will obtain their verbal consent to be approached by a member of the study staff. The study staff member will explain the study and conduct an informed consent discussion with the potential participant and their parent/guardian. The treating gastroenterologist will be available to address any questions or concerns that the potential participant and their parent/guardian may have about participating in the study.

Study visits and procedures are timed to coincide with regularly scheduled follow-up visits and collection of biospecimens that would occur as per standard of care for children and adolescents being treated for active Crohn's disease. This design is expected to minimize the burden of study participation for the subject and their parent/guardian and to improve the adherence to the study visit schedule. If needed, a study timepoint window of +/- 5 days is allowed for all visits/questionnaires/sampling.

Direct incentives will not be offered to participants or their parent/guardian.

6 STUDY INTERVENTION

6.1 STUDY INTERVENTION(S) ADMINISTRATION

6.1.1 STUDY INTERVENTION DESCRIPTION

The antibiotics to be used in this study are azithromycin and metronidazole. Both drugs are FDA-approved and commercially available, most recent product labels are available at the following URLs:

Azithromycin:

https://www.accessdata.fda.gov/drugsatfda_docs/label/2017/050670s032,050710s046,050711s043,050784s030lbl.pdf

Metronidazole:

https://www.accessdata.fda.gov/drugsatfda_docs/label/2015/012623s066lbl.pdf

Azithromycin (also Zithromax, Zmax) is a macrolide antibacterial drug indicated for mild to moderate infections caused by designated, susceptible bacteria:

- Acute bacterial exacerbations of chronic bronchitis in adults
- Acute bacterial sinusitis in adults
- Uncomplicated skin and skin structure infections in adults
- Urethritis and cervicitis in adults
- Genital ulcer disease in men
- Acute otitis media in pediatric patients
- Community-acquired pneumonia in adults and pediatric patients
- Pharyngitis/tonsillitis in adults and pediatric patients

Metronidazole (also Flagyl) is an oral formulation of the synthetic nitroimidazole antimicrobial, 2-methyl-5-nitro-1H-imidazole-1-ethanol indicated for infections strongly suspected to be caused by bacteria, particularly in the treatment of serious infections caused by susceptible anaerobic bacteria.

- Symptomatic or asymptomatic Trichomoniasis (*T. vaginalis*) infection in females and male and asymptomatic sexual partners. T
- Acute intestinal amebiasis (amebic dysentery) and amebic liver abscess.
- Anaerobic bacterial infections, in a mixed aerobic and anaerobic infection, antimicrobials appropriate for the treatment of the aerobic infection should be used in addition to metronidazole.
 - INTRA-ABDOMINAL INFECTIONS, including peritonitis, intra-abdominal abscess, and liver abscess, caused by *Bacteroides* species including the *B. fragilis* group (*B. fragilis*, *B. distasonis*, *B. ovatus*, *B. thetaiotaomicron*, *B. vulgatus*), *Clostridium* species, *Eubacterium* species, *Peptococcus* species, and *Peptostreptococcus* species.
 - SKIN AND SKIN STRUCTURE INFECTIONS caused by *Bacteroides* species including the *B. fragilis* group, *Clostridium* species, *Peptococcus* species, *Peptostreptococcus* species, and *Fusobacterium* species.
 - GYNECOLOGIC INFECTIONS, including endometritis, endomyometritis, tubo-ovarian abscess, and postsurgical vaginal cuff infection, caused by *Bacteroides* species including

the *B. fragilis* group, *Clostridium* species, *Peptococcus* species, *Peptostreptococcus* species, and *Fusobacterium* species.

- BACTERIAL SEPTICEMIA caused by *Bacteroides* species including the *B. fragilis* group and *Clostridium* species.
- BONE AND JOINT INFECTIONS, (as adjunctive therapy), caused by *Bacteroides* species including the *B. fragilis* group.
- CENTRAL NERVOUS SYSTEM (CNS) INFECTIONS, including meningitis and brain abscess, caused by *Bacteroides* species including the *B. fragilis* group.
- LOWER RESPIRATORY TRACT INFECTIONS, including pneumonia, empyema, and lung abscess, caused by *Bacteroides* species including the *B. fragilis* group.
- ENDOCARDITIS caused by *Bacteroides* species including the *B. fragilis* group.

